METHODOLOGY: This is a Phase I, randomised, double-blind, placebo-controlled, parallel group, single-centre study involving 45 healthy participants. The aim is to evaluate a combination vaccine against enteric fever comprising the live attenuated Salmonella strain ZH9 (previously tested in a number of clinical trials as a typhoid vaccine) and its modified derivative, ZH9PA, in which the typhoid antigens LPS O:9 and Flagellin H:d have been substituted by the Paratyphi A antigens, LPS O:2 and Flagellin H:a. ZH9PA has not previously been tested in humans; therefore, the first two cohorts comprise a dose escalation of this component alone, followed by a final cohort in which the combination is tested at a single dose level. The study will remain fully blinded until Day 70, when a stool sample is taken to assess if participants are shedding the bacterial strains of the vaccine in their faeces. The Investigators and the Monitor may be unblinded to the treatment allocation of participants who have a stool culture positive for any Salmonella strain, as it will be presumed to be one of the vaccine strains, and the participant will receive a course of antibiotics.
NUMBER OF PARTICIPANTS: 45 healthy participants 18 to 45 years of age, inclusive.

INCLUSION CRITERIA:**To be confirmed at Screening**

1. Healthy male and female participants 18 to 45 years of age, inclusive.
2. Female participant of childbearing potential willing to use 2 effective methods of contraception, i.e., established method of contraception + condom, if applicable (unless of non-childbearing potential or where abstaining from sexual intercourse is in line with the preferred and usual lifestyle of the participant) from the first dose until 2 months after the last dose of IMP.
3. Female participant of non-childbearing potential. *For the purposes of this study, this is defined as the participant being amenorrhoeic for at least 12 consecutive months or at least 4 months post-surgical sterilisation (including bilateral fallopian tube ligation or bilateral oophorectomy with or without hysterectomy).*
4. Female participant of childbearing potential or non-childbearing potential with a negative pregnancy test at Screening.

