Participants will be admitted to the Clinical Unit on the morning of Day 21, with assessments performed as per [Table 10.7.1](#). Following a 90-min fast prior to dose administration, participants will receive the second dose, and then continue to fast for a further 90 mins post dose administration; water will be allowed. Following the completion of the 4h post-dose assessments and at the discretion of the Investigator, the participants will be discharged from the Clinical Unit. Participants will return to the Clinical Unit on Day 24 for safety assessments as per [Table 10.7.1](#). For the 7 days following the second dosing visit (Day 22 to Day 28) participants will be required to record their body temperature at home twice a day, i.e. once in the morning and once in the evening (a thermometer and a diary will be provided to record body temperature). Participants will return to the Clinical Unit on Day 28 with the diary and to give a blood sample for the PBMC/ALS assay; assessments will be performed as per [Table 10.7.1](#).

Participants will be admitted to the Clinical Unit on the morning of Day 42, with assessments performed as per [Table 10.7.1](#). Following a 90-min fast prior to dose administration participants will receive the third dose, and then continue to fast for a further 90 mins post dose administration; water will be allowed. Participants will return on Day 45 for safety assessments as per [Table 10.7.1](#). For the 7 days following the third dosing visit (Day 43 to Day 49) participants will be required to record their body temperature at home twice a day, i.e. once in the morning and once in the evening (a thermometer and a diary will be provided to record body temperature). Participants will return to the Clinical Unit on Day 49 with the diary and to give a blood sample for the PBMC/ALS assay; assessments will be performed as per [Table 10.7.1](#).

Participants will return to the Clinical Unit on Day 70 to provide a stool sample for bacteriology. If the stool sample is positive for any *Salmonella* strain at Day 70, it will be presumed to be one of the vaccine strains, and participants will be asked to return to the Clinical Unit to receive a course of antibiotic therapy. Participants who receive a course of antibiotics will be required to provide a repeat stool sample for bacteriology testing on Day 84, to confirm that shedding of the vaccine strains has ceased, as per [Table 10.7.1](#).

Post-Study Follow-Up (Day 85 to Day 224)

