10.3 Discussion of Study Design, including the Choice of Control Groups

This is a Phase I, first in human, randomised, double-blind, placebo-controlled, parallel group, study. Randomised, double-blind studies are the gold standard methodology to assess the safety, tolerability and efficacy of products and therefore, this design has been used for this study. In the case of this study, it will remain fully blinded until Day 70, when a stool sample is taken to assess if participants are shedding the bacterial strains of the vaccine in their faeces. The Investigators and the Monitor will be unblinded to the treatment allocation of participants who have a positive result for *Salmonella* and the participant will receive a course of antibiotics.

No benefit to participants is expected, as efficacy has not been evaluated for the ZH9/ZH9PA combination or for ZH9PA on its own; therefore, use of placebo as the control is considered acceptable in the healthy participants participating in the study. The use of the placebo control allows an assessment of the immune response and provides a background incidence of adverse events.

Previous work with ZH9 has shown that the double mutation does appropriately attenuate the bacteria, however it is known that the bacterial strains that make up the vaccine can be shed in the stools of participants. The vaccine strains are genetically modified organisms, and as such it is necessary to reduce environmental exposure and stool cultures are taken to ensure that participants are not shedding.

There remains a theoretical risk of the vaccine strains causing a systemic infection and so body temperatures will be taken for 7 days post each dose of vaccine. The vaccine strains are

sensitive to several antibiotics, which can be used to treat an infection in the unlikely event such an event occurs.

Three doses are to be studied, as vaccines usually require more than one dose to induce a robust immune response.

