10.5.5 Removal of Participants from Therapy or Assessment

Each participant will be informed of his/her right to withdraw from the study at any time and for any reason.

An Investigator will withdraw a participant from the study at any time for any of the following reasons:

- If a participant experiences a serious or intolerable AE, that prevents him/her from continuing participation in the study.
- If a participant incurs a significant protocol violation which impacts on his/her safety or the scientific integrity of the study (this will be discussed on a case-by-case basis with the Sponsor).
- At the request of the Sponsor.
- If it is considered that the participant's health is compromised by remaining in the study or the participant is not sufficiently cooperative.
- If a participant is lost to follow-up.

Participants who meet one or more of the following stopping criteria will receive no further doses of the study vaccine but will be followed up for safety:

- Severe systemic reaction, e.g., anaphylaxis.
- Persistent febrile reaction ($\geq 38.5^{\circ}\text{C}$ for ≥ 12 hours) at the Investigator's discretion
- SAE related to the study agent (serious adverse reaction (SAR) or suspected unexpected serious adverse reaction (SUSAR))

The medical safety of the participant is of paramount importance when discussing study continuation.

The reasons for any participant withdrawal will be recorded on the study completion form of the electronic case report form (eCRF).

If a participant is withdrawn or chooses to withdraw from the study for any reason every possible effort will be made to perform the evaluations described for the post-study follow-up (see [Table 10.7.1](#)). The data collected from withdrawn participants will be included in the study report.

In the event of any abnormalities considered to be clinically significant, participants will be followed up with appropriate medical management until values are considered to be clinically acceptable. Referral or collaborative care will be organised if considered necessary.

A total of 45 participants are required to complete the study. Participants who withdraw from the study before receiving any IMP will be replaced. Participants who are withdrawn from the study due to significant drug-related AEs will not be replaced. Replacement of all other participants withdrawn from the study after receiving IMP will be decided on a case-by-case basis by the Principal Investigator (or deputy) and Sponsor.

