If the blind needs to be broken for an individual participant, the date and reason will be recorded in the participant's eCRF. The Investigator will not reveal the unblinded treatment code to any other member of the clinical team involved in the study or to the Study Monitor. If the code is broken for any individual participant, the participant will be withdrawn from the study and the procedures accompanying withdrawal performed. If the code is broken without justification, this will be deemed a serious protocol deviation.

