Concomitant Medication	X	X	X	X	X	X	X	X	X	X	X	X	X	X	X

Study Flow Chart Footnotes:

All procedures on dosing days (Days 0, 21, 42) are to be completed prior to dosing (except post dosing vital signs and health check for discharge)

¹ The treatment period will be approximately 85 days duration, from the first dosing day (Day 0) until Day 84 (inclusive).

² Post-study follow-up telephone call will be performed on Days 154 and 224 after receiving the first dose of IMP (Day 0).

³ Eligibility will be confirmed prior to dose administration on Day 0, Day 21 and Day 42.

⁴ For female participants only.

⁵ For postmenopausal female participants only

⁶ At Day 0, Day 21, and Day 42, vital signs to be performed pre-dose and at 4 hours post-dose.

⁷ IMP will be administered fasted (90 mins prior to dose administration). Participants will fast for a further 90 mins post each dose administration. Participants in sentinel cohorts will be contacted by telephone approximately 24 hours following the Day 0 dose to assess their safety profile.

⁸ Participants to record body temperature twice daily at home for 7 days post administration of each dose of IMP.

⁹ Blood cultures to be performed to identify vaccine strains only if a participant experiences defined symptoms (e.g., fever greater than 37.8°C, white blood cell (WBC) >20x10⁹ cells/L, respiratory rate >25 breaths per min, pulse rate >130 beats per min (bpm)) or clinically indicated.

¹⁰ Participants will attend the Clinical Unit on Day 70 to provide a stool sample. If the stool sample is positive for any *Salmonella* strain at Day 70, it will be presumed to be one of the vaccine strains, and participants will be asked to return to the Clinical Unit to receive a course of antibiotic therapy, and a repeat stool culture will be obtained on Day 84 to confirm shedding of *Salmonella*, presumed to be one of the vaccine strains, has ceased.

¹¹ Samples to be collected prior to each dosing.

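### Section 10.6.9 withdraws any participant whose code is broken, yet Section 10.3 unblinds *Salmonella*-positive participants after Day 70 and Section 10.1 needs them back on Day 84

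*Combined protocol and SAP*

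**What the plan says.** Section 10.6.9 (Blinding) describes emergency unblinding and unblinding to treat an adverse event, both through sealed envelopes. It then states a general rule: "If the code is broken for any individual participant, the participant will be withdrawn from the study and the procedures accompanying withdrawal performed". It also limits disclosure by the Investigator, who "will not reveal the unblinded treatment code to any other member of the clinical team involved in the study or to the Study Monitor".

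Section 10.3 plans a further unblinding once the Day 70 stool result is known: "The Investigators and the Monitor will be unblinded to the treatment allocation of participants who have a positive result for" *Salmonella*. The synopsis makes the same step optional: "The Investigators and the Monitor may be unblinded to the treatment allocation of participants who have a stool culture positive for any" *Salmonella* strain.

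Section 10.1 expects these participants to continue: "Participants who receive a course of antibiotics will be required to provide a repeat stool sample for bacteriology testing on Day 84". The flow chart footnote in Section 10.7.1 agrees: "a repeat stool culture will be obtained on Day 84 to confirm shedding of" the presumed vaccine strain has ceased.

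Section 10.5.5 says what follows withdrawal: best efforts to perform the post-study follow-up evaluations, with data already collected included in the report. Section 10.1 defines post-study follow-up as Day 85 to Day 224 and fills it with telephone calls on Days 154 and 224. Separately, Section 10.5.5 says that participants who meet an individual stopping criterion, including a related SAE, "will receive no further doses of the study vaccine but will be followed up for safety".

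**The concern.** A rule that removes participants because their code was opened is applied, on its face, to people whose code the protocol itself plans to open. They are selected by a post-randomisation result, a positive stool, which the protocol presumes to be a vaccine strain. Missing Day 84 data would therefore be tied to treatment and to persistence of the vaccine organism, with almost none of it among placebo recipients.

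Day 84 matters for three reasons. It is the only serum time-point after the third dose, so the first secondary objective (response to three doses up to Day 84) depends on it. It closes the primary safety window. It is also the scheduled check that shedding has stopped. Sections 10.5.1, 10.5.2 and 10.5.4.3 end the male contraception, sperm donation and travel restrictions on a negative stool, and a withdrawn shedder has no further stool scheduled. A Day 84 sample that is not taken cannot be recovered at analysis.

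**Working it through.** There is no figure in the plan to reproduce: Section 10.9.2 says that the sample size has no formal basis, and no shedding rate is given. The check is mainly textual.

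**Step 1: can the rules be followed together?**
- Section 10.6.9: code broken → withdrawn from the study. No exception is written.
- Section 10.3: stool positive at Day 70 → allocation unblinded (synopsis: may be).
- Section 10.1 and the flow chart footnote: stool positive → antibiotics → repeat stool on Day 84.

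The result and the antibiotics come between Day 70 and Day 84, so an unblinding prompted by the result comes before the Day 84 visit. One unblinded positive participant is enough to make the rules incompatible.

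**Step 2: do the withdrawal procedures recover Day 84?** No. They point to post-study follow-up, which starts on Day 85 and consists of two telephone calls.

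**Step 3: what is lost and what is kept?** (Table 10.7.2, flow chart, Section 10.9.1.2)
- Serum Ig is drawn on Days 0, 21, 42 and 84. The Day 42 sample is taken before dose 3, so Day 84 is the only serum after dose 3. Lost.
- Day 84 biochemistry, haematology, examination and the clearance stool. Lost.
- All three doses, the Day 45 and Day 49 visits, Day 49 laboratory tests, temperature diaries and every ALS sample (Days 0, 7, 28, 49) precede Day 70. Kept.
- Safety Set (at least one dose) and PD Set (one dose and one post-baseline antibody value) membership. Kept.
- Seroconversion already shown at Day 21 or Day 42. Kept.

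**Step 4: how many?** Active participants: 6 + 12 + 12 = 30. Placebo: 3 + 6 + 6 = 15. Let *s* be the proportion of vaccinees positive at Day 70, which is an assumption. Expected losses are *n·s*, and the chance of at least one among 30 is 1 − (1 − *s*)^30.

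| *s* (assumed) | expected of 30 | expected per arm of 12 | chance of ≥1 of 30 |
|---|---|---|---|
| 2% | 0.6 | 0.24 | 0.455 |
| 5% | 1.5 | 0.6 | 0.785 |
| 10% | 3.0 | 1.2 | 0.958 |
| 20% | 6.0 | 2.4 | 0.999 |
| 30% | 9.0 | 3.6 | 1.000 |

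This takes all positives to be unblinded and *s* to be the same in every arm.

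**Step 5: illustration of bias at Day 84 only.** Suppose shedders' Day 84 titres are *r* times those of non-shedders and a fraction *f* of the arm sheds. The log GMT of the full arm is log *m* + *f*·log *r*; among those remaining it is log *m*. The ratio of remaining to true GMT is therefore *r*^(−*f*).
- *r* = 2: 2^(−0.02) = 0.99; 2^(−0.1) = 0.93; 2^(−0.3) = 0.81.
- *r* = 4: 4^(−0.02) = 0.97; 4^(−0.1) = 0.87; 4^(−0.3) = 0.66.
- *r* = 1: ratio 1, no bias.

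By-visit seroconversion at Day 84, with true rate 70% and 20% shedders: if all shedders convert, (0.70 − 0.20)/0.80 = 62.5% is observed. If shedders convert at the same 70%, (0.70 − 0.14)/0.80 = 70%, with no bias.

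**The case against.** The best reply is that the withdrawal sentence was never meant for Day 70. It follows the emergency and AE-treatment routes and stands next to a sentence about unjustified code breaks. The Day 70 unblinding is a planned step described elsewhere, and Section 10.1 and the flow chart expressly bring these participants back. The Monitor sentence points the same way: Section 10.6.9 withholds the code from the Monitor, whereas the Day 70 step reveals it. As a reading of intent this is plausible. But no passage limits the rule to those two routes, and its wording covers any individual participant. Site staff who follow it as written would withdraw the participant.

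Other parts of the reply stand, and they limit the point:
- A reader might infer that every shedder would be lost. Only Section 10.3 makes unblinding mandatory. The synopsis makes it optional, and antibiotics follow from the stool result without a code break.
- A reader might infer that the primary safety evaluation collapses. It does not. The post-dose visits are over by Day 49. What is at risk is the Day 84 visit and full AE collection between withdrawal and Day 84. Section 10.5.5 also keeps clinically significant abnormalities under follow-up.
- A reader might apply the fall from 70% to 62.5% to the seroconversion endpoint. Section 10.9.1.1 counts a 4-fold rise at any time after vaccination, so conversions by Day 42 survive. The example fits only the by-visit comparison in Section 10.9.1.3.4.
- Withdrawal after a code break made to treat an AE is a stated rule that the Day 70 passages do not contradict.

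**Conclusion.** The contradiction is in the text and should be removed by amendment before any participant reaches Day 70. As written, Section 10.6.9 withdraws participants whom Section 10.3 unblinds and Section 10.1 needs on Day 84. The losses would fall almost only in active arms of 6, 12 and 12, where even one or two missing Day 84 results matter.

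The size cannot be derived. The documents give neither a Day 70 shedding rate nor any link between shedding and titre. The expected counts (0.6 to 9 of 30) and GMT ratios (0.99 to 0.66) follow from assumed inputs and show sensitivity; they are not evidence that the trial would be biased by that amount. They concern by-visit Day 84 results only. That shedders respond more strongly is also an assumption. If they do not, the cost is precision, an incomplete closing safety visit and a missing clearance stool.

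Two related inconsistencies need resolving: whether the Day 70 unblinding is mandatory or optional, and whether the Monitor may know the code. A third is narrower. Section 10.5.5 promises safety follow-up after a related SAE, while Section 10.6.9 would withdraw that participant from the study if the code were opened.

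**What to change.** In Section 10.6.9, add wording to this effect:

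> Planned unblinding after a positive Day 70 stool culture is not a reason for withdrawal from the study. The participant completes the Day 84 and post-study follow-up assessments and remains in the Safety and PD Sets. The date, the reason and the persons unblinded are recorded, and assessments made after unblinding are flagged in the data.

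In the same amendment:
- Align the synopsis and Section 10.3 on whether unblinding of stool-positive participants is optional or mandatory.
- Reconcile the ban on telling the Study Monitor in Section 10.6.9 with the synopsis and Section 10.3.
- For code breaks made to treat an AE or after a related SAE, the sponsor and investigator should reconcile Section 10.6.9 with the safety follow-up in Section 10.5.5, preferably keeping scheduled data collection. Whether further vaccine is given after such a code break is for them to settle and should be stated separately.

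The cost is a few sentences in one amendment. No visit, sample or participant is added, because the Day 84 assessments are already scheduled.

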10.6.10 Prior and Concomitant Therapy

Prior Medication: Prescription or non-prescription drugs, should not be taken within 28 days (or 5 half-lives (whichever is longer)) prior to receiving the first dose of IMP, unless in the opinion of the Investigator and Sponsor's Responsible Physician the medication will not interfere with the study procedures or compromise participant safety. Prescription or non-prescription drugs taken during the 28 days before receiving the first dose of IMP, and the reason for taking them, will be noted in the participant's eCRF.

Inclusion of participants who have taken prior medication will be reviewed on a case-by-case basis in relation to the safety aspects and objectives of this study.

Concomitant Medication: Prescription or non-prescription drugs should not be taken throughout the duration of the study, with the exception of paracetamol (which may be taken as an analgesic to a maximum of 2 grammes (g) in 24 h).

If intake of ANY medication is necessary during the study, the daily dosage, duration and reasons for administration will be recorded in the concomitant medication section of the participant's eCRF.

Prohibited Medications:

28 days prior to first dose (Day 0) to Day 49:

- Prescription and Non-prescription drugs (exception of 2 g per 24 hours of paracetamol).

28 days prior to first dose (Day 0) to 28 days following the third dose on Day 42, i.e. Day 70:

- Antibiotics

Participants requiring antibiotics to treat an infection from Day 0 to Day 49 will be followed for safety but will not receive further doses of IMP.

28 days prior to first dose (Day 0) to Day 84:

- Non-steroidal anti-inflammatory drugs (NSAIDs) (participants will be advised to avoid NSAIDs if possible)
- Steroids
- Immunosuppressants

- Vaccines

10.6.11 Treatment Compliance

Each dose of IMP will be taken under supervision and compliance will be documented. The exact time a participant starts to drink the IMP and the exact time a participant finishes drinking the IMP will be recorded on the participant's eCRF.

10.7 Safety Variables

10.7.1 Safety Measurements Assessed and Flow Chart

A schedule of study assessments is provided in [Table 10.7.1](#).

Simbec-Orion personnel who have been appropriately trained will carry out study procedures. Where more than 1 procedure is scheduled for the same time-point, the following order of priority will apply:

1. Safety and pharmacodynamic (PD) blood sampling
2. Vital signs and 12-lead ECG (a window of \pm 10 min in relation to the nominal time-point is allowed).
3. Urine collection for urinalysis, urine DOA and urine pregnancy (if applicable)

All baseline assessments will be performed prior to dosing on each dosing day.

Table 10.7.1 Study Flow Chart

	Screening	Treatment Period ¹												Post-Study Follow-Up Telephone Call ²	
		0	1	2	3	4	6	7	10	12	22	32			
Week		0	1	2	3	4	6	7	10	12	22	32			
Day	-28 to -1	0	3	7	14	21	24	28	42	45	49	70	84	154	224
Visit	1	2	3	4	5	6	7	8	9	10	11	12	13	14	15
Visit Window (days)	N/A	+/-0	+/-1	+/-1	+/-1	+/-0	+/-1	+/-1	+/-0	+/-1	+/-1	+/-1	+/-7	+/-7	+/-7
Informed Consent	X														
Inclusion/Exclusion ³	X	X				X		X							
Demographics	X														
Height / Weight / BMI	X												X (weight only)		
Medical History & Concurrent Conditions	X														
Virology Tests	X														
Urine DOA (including Alcohol and Cotinine) ³	X	X ¹¹			X ¹¹			X ¹¹							
Pregnancy ^{3, 4}	X (serum)	X (urine) 11			X (urine) 11			X (urine) 11					X (serum)		
FSH ⁵	X														
Biochemistry ³	X	X ¹¹		X		X ¹¹		X	X ¹¹		X		X		
Haematology ³	X	X ¹¹		X		X ¹¹		X	X ¹¹		X		X		
Urinalysis	X		X			X			X				X		
Vital Signs ⁶	X	X	X	X	X	X	X	X	X	X			X		
Physical Examination	X												X		
General Health Check		X				X			X						
12-Lead ECG	X												X		
Placebo training	X														
Vaccine administration ⁷		X				X			X						

	Screening	Treatment Period ¹												Post-Study Follow-Up Telephone Call ²	
		0	1	2	3	4	6	7	10	12	22	32			
Week		0	1	2	3	4	6	7	10	12	22	32			
Day	-28 to -1	0	3	7	14	21	24	28	42	45	49	70	84	154	224
Visit	1	2	3	4	5	6	7	8	9	10	11	12	13	14	15
Visit Window (days)	N/A	+/-0	+/-1	+/-1	+/-1	+/-0	+/-1	+/-1	+/-0	+/-1	+/-1	+/-1	+/-7	+/-7	+/-7
Twice-Daily Temperature Records ⁸															
Blood culture ⁹															
Stool bacteriology (vaccine strains) ¹⁰											X	(X)			
Administration of antibiotics ¹⁰											(X)				
Blood sample for serum Ig responses ¹¹		X			X			X			X				
PBMC collection for ALS assay ¹¹		X		X				X			X				
Adverse Events		X	X	X	X	X	X	X	X	X	X	X	X	X	X
Concomitant Medication	X	X	X	X	X	X	X	X	X	X	X	X	X	X	X

Study Flow Chart Footnotes:

All procedures on dosing days (Days 0, 21, 42) are to be completed prior to dosing (except post dosing vital signs and health check for discharge)

¹ The treatment period will be approximately 85 days duration, from the first dosing day (Day 0) until Day 84 (inclusive).

² Post-study follow-up telephone call will be performed on Days 154 and 224 after receiving the first dose of IMP (Day 0).

³ Eligibility will be confirmed prior to dose administration on Day 0, Day 21 and Day 42.

⁴ For female participants only.

⁵ For postmenopausal female participants only

⁶ At Day 0, Day 21, and Day 42, vital signs to be performed pre-dose and at 4 hours post-dose.

⁷ IMP will be administered fasted (90 mins prior to dose administration). Participants will fast for a further 90 mins post each dose administration. Participants in sentinel cohorts will be contacted by telephone approximately 24 hours following the Day 0 dose to assess their safety profile.

⁸ Participants to record body temperature twice daily at home for 7 days post administration of each dose of IMP.

⁹ Blood cultures to be performed to identify vaccine strains only if a participant experiences defined symptoms (e.g., fever greater than 37.8°C, white blood cell (WBC) >20x10⁹ cells/L, respiratory rate >25 breaths per min, pulse rate >130 beats per min (bpm)) or clinically indicated.

¹⁰ Participants will attend the Clinical Unit on Day 70 to provide a stool sample. If the stool sample is positive for any *Salmonella* strain at Day 70, it will be presumed to be one of the vaccine strains, and participants will be asked to return to the Clinical Unit to receive a course of antibiotic therapy, and a repeat stool culture will be obtained on Day 84 to confirm shedding of *Salmonella*, presumed to be one of the vaccine strains, has ceased.

¹¹ Samples to be collected prior to each dosing.

